Potential participants will be asked to repeat back understanding of this material as necessary. Individuals will not be permitted to participate if there is any question as to whether s/he is able to provide informed consent.

The participant will then be asked to sign and date the ICF. Research staff will also date and sign the ICF. All participants will be offered a copy of the signed ICF for their records.

A scanned copy of the consent form and an enrollment note template will be sent to the VAPSHCS Research Compliance Officer (RCO) as per VAPSHCS guidelines. In addition, a note of enrollment will be made in CPRS.

Research staff will file the original copy of the consent form in [name] office, separate from data collected during screening and subsequent data collected during participation in the study.

Participants will also be provided a revised response key to help answer questions asked during the telephone assessment periods for the sub-study.

Research staff will complete a sub-study specific enrollment case report form that will be filed with study data. In addition, research staff will complete a revised "documenting the consent process" form for each enrolled participant that will be filed with the signed consent form.

Telephone Assessment

A research staff member will ask each participant two questions about how much the participant agrees with certain statements about his/her sleep, as well as two questions about how confident the participant is about carrying out certain sleep behaviors. These questions will be asked during the pre-treatment assessment period, 4-week assessment period, post-treatment assessment period, and the assessment period that takes place 3 months following the end of treatment. The questions will take about 5 minutes to complete. The pre-treatment assessment period may be repeated if the participant does not start treatment within four weeks of completing the original pre-treatment assessment period.

Sleep/Wake Diary

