The goal of mediation analyses is to examine whether group assignment (determined by randomization at baseline) impacts the change in pain intensity (primary outcome) from baseline to post-treatment through indirect effects on the hypothesized mediators (measured midway

between baseline and post-treatment). Our potential mediators have been identified a priori and are shown in the table of measures (Table 4).

To evaluate the association between intervention type, potential mediating factors, and change in pain intensity, we will first run models with individual mediators to get unadjusted estimates and to estimate the degree of confounding in subsequent multivariate models. Per Hayes & Rockwood's 2017 recommendations, we will test multiple mediators in the same model, to more accurately reflect our theoretical understanding of parallel biological and psychological mediating processes, and to facilitate comparison of the size of indirect effects through different mediators. Mediators to be included in the model include change in EEG composite scores for theta, alpha, beta, and gamma bandwidths, pain acceptance, catastrophizing, mindfulness, therapeutic alliance, and skill practice. Also per the recommendations of Hayes and Rockwood (2017), we will compute bootstrap confidence intervals for the indirect effects. All mediation analyses will be done using PROCESS, a free downloadable add-on available for SPSS and SAS (the analysis packages we will use for the study's data analysis). PROCESS includes the computational code to generate a primary estimate for the mediation model which represents the indirect, or mediated effect, and allows for inclusion of moderator variables.

Our study is longitudinal and, in addition to posttreatment assessments, we have collected data at 3- and 6-months post-treatment on outcomes and all other variables (mediators and moderators). While the approach used in the PROCESS software can be somewhat adapted for longitudinal analysis, the most appropriate analysis would be longitudinal structural equations models, particularly latent growth models (e.g., Goldsmith et al. 2018). These models require specialized software such as AMOS or LISREL and are beyond the scope of our exploratory aims. If we are able to access such statistical resources in the future, however, we would like to leverage this dataset for these exploratory purposes.

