Additional covariate and mechanism variables will be captured to explain sleep findings more completely. Routine and “as required” (PRN) medications for each participant will be recorded on the 7-day sleep log to aid in understanding how sleep or pain medicines relate to sleep measurements. Sleep data will be analyzed for relationships with data already collected within the parent grant, including depression scores and self-report of new self-hypnosis and mindfulness meditation skills practiced. In addition to the mediators already examined within the parent grant, sleep self-efficacy will be explored using a 4-item Sleep Self-Efficacy and Control Scale.⁸⁹ These mediator variables will be related to the sleep outcomes (not the pain outcomes as those are already analyzed for covariates in the parent grant) by including them as covariates in mixed-effects ANOVA, controlling for condition and time point. These will be exploratory analyses where type II error is more problematic than type I error; therefore no type I error threshold correction is envisioned. Mediator analysis results will be explicitly reported as exploratory.

D6y. Missing Data

Analyses to identify potential patterns in missing outcome data will be conducted to determine if they are missing at random (“ignorable”). Missingness at random is not testable, but we can look at the variables that were observed in both, group with missing and without missing outcomes data. No association between observed variables and the group (missing vs. no missing) will be considered an indication that the data is missing at random. In addition, we will also look at the reported reasons for missing values (when available). If we can assume missing at random data, we will use multiple imputation procedures. Currently, two methods are used when the data is considered not missing at random: Heckman’s selection models and pattern-mixture models, both of which model the joint distribution of the outcome and the missing mechanism. In the case of non-ignorable missing data, we will use both methods as a sensitivity analysis. If less than 5% of the data is missing and we can assume ignorable missing data, the following analysis will be performed.

D6z. Power Analyses

We performed power analyses, reported below, to ensure that the study had more than adequate power to test the hypothesis related to the effects of the treatments on the primary outcome (average pain intensity).

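### The sleep sub-study's mediator analysis enters the mediator as a covariate in the sleep model, which shows association with sleep but cannot show mediation

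*Combined protocol and SAP*

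**What the plan says.** The sub-study text in D6x (Statistical Analyses) adds one mediator to those of the parent study: "sleep self-efficacy will be explored using a 4-item Sleep Self-Efficacy and Control Scale". It then states the outcome, "These mediator variables will be related to the sleep outcomes (not the pain outcomes as those are already analyzed for covariates in the parent grant", and the method, "by including them as covariates in mixed-effects ANOVA, controlling for condition and time point". On inference it says that "no type I error threshold correction is envisioned", and on labelling that "Mediator analysis results will be explicitly reported as exploratory".

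The main-study part of D6x, under Mediation analyses, works differently. Its goal is to see whether assignment affects pain change "through indirect effects on the hypothesized mediators", and its inference is that "we will compute bootstrap confidence intervals for the indirect effects", using PROCESS. That plan covers pain intensity, not sleep.

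On timing, D6s (Telephone Assessment) describes two agreement items and two confidence items about sleep: "These questions will be asked during the pre-treatment assessment period, 4-week assessment period, post-treatment assessment period", and again at 3 months. D6s does not name the scale. The item count and content match the 4-item self-efficacy scale in D6t, and I take them to be the same. Actigraphy and the sleep diary are collected before treatment, after treatment and at 3 months, but not at week 4.

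**The concern.** Mediation needs two links: treatment changes the mediator, and the mediator is related to the outcome given treatment. The coefficient of a covariate in the sleep model is the second link alone. The sub-study text plans no product of the two links, no comparison of the condition effect with and without the mediator, and no ordering of mediator before outcome.

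The missing link matters most for sleep self-efficacy, because no other part of the document tests whether treatment changed it. D6t justifies measuring it by asking whether taking up new skills raises confidence in managing one's sleep, which is the path left unestimated. Section J says the sub-study will inform on treatment mechanisms. A significant covariate under a mediator heading could be read as evidence of how HYP or MM work when it shows only that confident sleepers sleep better in every arm.

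**Working it through.** **1. The plan's own figure.** D6z (Power Calculations, Sub-Study) gives d = 15/26.3 = 0.57, one-sided alpha 0.05, power 80%, 39 per group. The normal formula is n = 2(z₀.₉₅ + z₀.₈₀)²/d² = 2(1.645 + 0.842)²/0.5703² ≈ 38.0, just above 38, so 39 after rounding up. The t-based solution is 38.7, also 39, with power 80.2% at 39 per group. The total is 3 × 39 = 117. The figure reproduces. The documents give no figure for the mediator analysis itself.

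**2. What each analysis estimates.** For active arm k against ED:

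- Mediator model: M = a₀ + a₁·HYP + a₂·MM + baseline terms
- Sleep model: Y = c₀ + c₁·HYP + c₂·MM + b·M + baseline terms
- Indirect effect for arm k: aₖ × b

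The planned analysis tests b = 0. If treatment does not change M, then aₖ = 0 and the indirect effect is 0 × b = 0 for any b. The chance that the planned test is significant is then simply its power to detect b.

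**3. Illustration by simulation.** Inputs from the documents: 39 per arm, three arms, three time points and a random-intercept model. Assumptions that are mine: the mediator-sleep correlation r, within-person correlation 0.5, complete data, mediator and sleep matched by visit, and no treatment effect on the mediator or on sleep. There were 1,000 runs per row. The planned test is the mediator's coefficient at two-sided p < 0.05. The comparator is a 95% Monte Carlo interval for aₖ × b at post-treatment, baseline-adjusted.

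| Assumed r | Covariate significant | aₖ × b flagged, one comparison | Flagged, either comparison |
|---|---|---|---|
| 0 | 5% | 0% | 0% |
| 0.1 | 43% | 1% | 2% |
| 0.2 | 97% | 2% | 4% |
| 0.3 | 100% | 4% | 8% |
| 0.5 | 100% | 5% | 9% |

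With a real effect on the mediator (a = 0.6 SD, r = 0.3), the interval detects mediation in 76% of trials for one comparison.

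**4. Sensitivity to the design assumption.** If only one visit per person carried the information, Fisher's z gives power ≈ Φ(atanh(r)·√(117 − 3) − 1.96):

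- r = 0.1: Φ(0.1003 × 10.68 − 1.96) = Φ(−0.89) ≈ 19%
- r = 0.2: Φ(0.2027 × 10.68 − 1.96) = Φ(0.20) ≈ 58%

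The percentages move a good deal with the assumptions. The algebra in step 2 does not.

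**5. Limits of the comparison.** The simulated interval used the post-treatment mediator and normal draws. It did not use the week-4 mediator or a bootstrap, so the 76% should not be read as the power of the proposed analysis.

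**The case against.** The strongest reply is that the analysis is exploratory, is to be reported as such, and is described in associational terms. That limits the harm. It does not change the estimand: the exploratory label and the waived correction deal with multiplicity and strength of evidence, and the results are still called mediator results.

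Several stronger readings are tempting, and the documents do not support them:

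- *The plan would declare any correlate of sleep a mediator.* It states no decision rule, so this could happen but is not prescribed.
- *The treatment-to-mediator path is never estimated.* The main-study mediation models include it for pain acceptance, catastrophizing, mindfulness, therapeutic alliance, skill practice and EEG change. For these, only the indirect effect on sleep is missing. The path is wholly absent for sleep self-efficacy.
- *Mediator and sleep come from the same visit.* D6x does not say which mediator measurement enters the model. Matching by visit is an inference.
- *Depression will be presented as a mediator.* Table 4 lists it as a secondary outcome, and D6x names it in a separate sentence about relationships with parent-study data.
- *The simulated percentages are the plan's error rates.* They are the power of an association test under assumed correlations, and become false mediation findings only if significance is read as mediation.

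**Conclusion.** Wrong as written, with moderate to low severity. The stated method cannot show mediation of sleep by any variable. This rests on the definition of an indirect effect and on the text of D6x, not on any assumed number. The main-study method does not fill the gap because it is confined to pain.

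The size is illustrative. Under the three-time-point assumptions, a variable untouched by treatment is significant in 43% of trials at r = 0.1 and 97% at r = 0.2, against 1% to 5% per comparison for an indirect-effect interval over r = 0.1 to 0.5. The hypotheses and sample size for sub-study Aims 1 and 2 are not affected.

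**What to change.** In the sub-study part of D6x, replace the covariate method as follows.

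- **Sleep self-efficacy.** Estimate the indirect effect on post-treatment sleep, adjusted for pre-treatment sleep, through week-4 self-efficacy, adjusted for its pre-treatment value. Report it for HYP versus ED and MM versus ED with bootstrap confidence intervals, and report the treatment effect on self-efficacy alongside.
- **Parent mediators with a pre-treatment and an in-treatment value.** Do the same. By Table 5 these are pain acceptance, catastrophizing, mindfulness, subjective happiness and BIS/BAS.
- **Everything else.** Report as correlates of sleep. Skill practice and therapeutic alliance have no pre-treatment value in Table 5, EEG has no in-treatment value, and depression is not a listed mediator.

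The cost is a few lines of text and a little more analysis. The self-efficacy items are already collected before treatment and at week 4, and PROCESS is already planned. With one mediator time and one outcome time, the longitudinal structural models that the main study places beyond its scope are not needed. Power is lower than for a plain association test, and 3-month sleep is not covered unless added as a second outcome. The results remain exploratory. If the sponsor prefers no new analysis, renaming the whole analysis as one of correlates of sleep removes the mislabelling but leaves the mechanism question unanswered.

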not testable, but we can look at the variables that were observed in groups with and without missing outcomes data. No association between observed variables and the group (missing vs. no missing) will be considered an indication that the data are missing at random. In addition, we will look at the reported reasons for missing values when available. If we can assume data are missing at random, we will use multiple imputation procedures. If there appear to be non-random missing outcomes data, we will use two methods designed to account for this: Heckman's selection models and pattern-mixture models, both of which model the joint distribution of the outcome and the missing mechanism. In the case of non-ignorable missing data, we will use both methods as a sensitivity analysis. If less than 5% of the data is missing and we can assume ignorable missing data, the following analysis will be performed.

Hypothesis 1 states that Veterans randomly assigned to receive eight group sessions of HYP or MM will report significantly greater pre- to post-treatment decreases in average pain than Veterans receiving eight sessions of ED. The response variable will be change in average pain intensity score from pre- to post-treatment (Pre-treatment score – Post-treatment score). This response variable will be analyzed using an analysis of covariance (ANCOVA) with treatment condition (HYP, MM, ED) as the explanatory variable and the baseline pain as a covariate.

Support for Hypothesis 1 would emerge if a significant treatment main effect is present after adjusting for the baseline covariate, and subsequent post-hoc analyses indicate larger baseline to post-treatment decreases in pain intensity in the HYP and MM conditions, relative to the ED condition. The overall significance level for the test of the null hypothesis that all three treatments have equal effect will be set to 0.05.

Although we anticipate that HYP and MM will have similar effects on the primary outcome variable, these analyses will also allow us to compare the relative effects of HYP and MM with each other, as part of the exploratory aims/analyses.

Pairwise comparisons of the treatment groups will be performed using Tukey method (see for example, Analysis of Messy Data Volume 1: Designed Experiments, Second Edition, by GA Milliken and DE Johnson. 2009, chapter 3).

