Perceived global improvement is a secondary outcome measure but unlike the other secondary outcome measures it was not measured at baseline, hence a slightly different approach will be used for this secondary outcome measure. Instead of a change score, we will simply use ANOVA to compare perceived global improvement with treatment condition as the independent variable.

To assess the effect of each treatment on post-treatment ratings of global satisfaction (which has only 5 categories), we will use an ordinal polytomous logistic regression. Because we anticipate that *both* HYP and MM will have significant beneficial effects on outcomes, we do not anticipate large differences between these two interventions in the outcome measures. However, we think that it would be important to estimate differences in outcome between the two active treatments for descriptive purposes. To do so, we will perform pairwise post-hoc tests to compare the means of the three groups.

We will report both the p-value and effect sizes for the tests between the two conditions (HYP and MM) on outcomes. While the study was not powered to simultaneously test for the primary and secondary outcomes, it is reasonable to assume that the sample size of 80 participants per condition (determined to adequately power the primary hypotheses) will allow for reliable estimates of the effect sizes for secondary outcomes as well.

Longer-term effects of HYP and MM, relative to ED.

As part of our exploratory aims, we plan to assess the extent to which change in pain intensity, the primary outcome, is maintained at 3 and 6 months post-treatment, and to see if longer term changes in pain intensity differ between HYP and MM compared to ED. To assess this, we propose to use a Generalized Estimating Equations (GEE) approach, which accounts for the correlated nature of the data due to multiple observations of the same person over time. Response variables over time will be the change from pre-treatment to post-treatment, and pre-treatment to 3- and 6- months follow-ups, with intervention group and follow-up time as the main factors of interest (including a Group X Time interaction), and the pre-treatment value as the covariate. For the correlation matrix, we will assume an unstructured format, since there was no a priori reason to use a more structured matrix format. We will repeat these analyses for the secondary outcome measures mentioned above.

Mediation analyses.

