Power to test the primary study hypothesis. The primary study outcome variable is change in average pain intensity, as represented by the difference between the baseline and post-treatment average pain intensity measures. We have used this measure successfully in numerous previous trials.^{41, 42, 52, 105, 106} Anticipated effects for HYP are based on the changes observed in our previous HYP trials using the 0-10 NRS measure, plus our pilot study of HYP for low back pain treatment, reported in the

'Preliminary findings' section.

Anticipated effect sizes for MM are based on published studies of the effects of treatments that involve mindfulness that used 0-10 NRS measures.

Assuming a decrease in pain score of 0.3 points for the education group, 0.8, 1 and 1.4 for the HYP, and 0.6, 0.8 and 1 for MM, we calculated the sample size to find differences between pre-post treatment difference scores, with an alpha of 0.05, power of 0.80, and varying the standard deviation (SD) from 0.15 to 1 (to cover values observed) when using an ANOVA. Sample sizes of 80 completers per condition (total = 240) will have at least 80% power, even at the largest standard deviation.

Power for secondary and exploratory analyses.

The sample size calculations above take into consideration only the primary hypothesis of interest (that different treatment have different effects in changing pain intensity), which is the most important result this study can provide for the person affected with chronic pain. However, the sample size of this study is relatively large and will provide extremely useful and important information regarding secondary outcomes, mediators and moderators associated with pain intensity and EEG. The results will form the basis for continuing research not only to find treatments that are efficacious, but also to hypothesize mechanisms of action, which will be crucial in designing future studies.

Power Calculations (Sub-Study)

We focus our power calculations on the most innovative aspect of the supplemental study, that is, the objective measurement of sleep by means of wrist actigraphy in the context of non-pharmacological pain treatments.

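### The stated 80% power is for the three-group omnibus test, not for the stricter rule that decides Hypothesis 1; at the smallest planned mindfulness effect and SD 1, that rule has about 30% power

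*Combined protocol and SAP*

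**What the plan says.** **Power.** Section D6z, in the paragraph on power for the primary study hypothesis, assumes an ANOVA on change scores and concludes: "Sample sizes of 80 completers per condition (total = 240) will have at least 80% power, even at the largest standard deviation". The opening of D6z claims "more than adequate power to test the hypothesis related to the effects of the treatments on the primary outcome". D6x, in the paragraph on secondary outcomes, refers back to a "sample size of 80 participants per condition (determined to adequately power the primary hypotheses".

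**Hypothesis and decision rule.** D6x words Hypothesis 1 as follows: "Veterans randomly assigned to receive eight group sessions of HYP or MM will report significantly greater pre- to post-treatment decreases in average pain" than Veterans given ED. The Précis and section A2 also join the two arms with 'or'. Support requires a significant treatment effect in the ANCOVA and, in addition, that "subsequent post-hoc analyses indicate larger baseline to post-treatment decreases in pain intensity in the HYP and MM conditions, relative to the ED condition". The only level given is for the "test of the null hypothesis that all three treatments have equal effect will be set to 0.05". On the follow-up tests the plan says: "Pairwise comparisons of the treatment groups will be performed using Tukey method". It gives no level for them, and no power for the full rule or for either contrast with ED.

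**The concern.** The sample size is justified by one test and the primary hypothesis is decided by another. A significant F-test shows only that the three means are not all equal. The rule in D6x goes on to ask about HYP against ED and MM against ED. A reader who meets the 80% under a heading about the primary hypothesis will take it as the chance that Hypothesis 1 is supported if the planned effects are true.

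Two things are at stake. First, if both contrasts must be significant, the real chance can be far below 80% at effects the plan itself lists. A non-significant MM result could then be taken as well-powered evidence of no benefit. Second, the hypothesis says 'or' while the rule says 'and'. A result with HYP significant and MM not could therefore be reported as supporting or not supporting the primary hypothesis, with the choice made after the data are seen.

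**Working it through.** **Inputs from D6z:** 80 completers per arm; alpha 0.05; mean decreases of 0.3 for ED, 0.8, 1.0 or 1.4 for HYP, and 0.6, 0.8 or 1.0 for MM; largest SD 1. **From D6x:** omnibus test at 0.05, Tukey for pairs. **Assumed, because not stated:** Tukey family-wise level 0.05; every HYP value crossed with every MM value; no reduction in SD from the baseline covariate.

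**Step 1: the plan's own figure.** Omnibus power uses λ = n Σ(μᵢ − μ̄)² / SD². In the weakest case (0.3, 0.8, 0.6) the mean is 0.567, the squared deviations sum to 0.0711 + 0.0544 + 0.0011 = 0.1267, and λ = 80 × 0.1267 = 10.13. With 2 and 237 df the critical F is 3.034 and the noncentral F gives 81.6%. The other eight combinations give 91% or more. The stated figure reproduces.

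**Step 2: each contrast with ED.** SE = SD √(2/n) = √(2/80) = 0.158. The Tukey critical t is the studentized range point divided by √2, which is 2.359. At SD 1 an observed difference must therefore exceed 2.359 × 0.158 = 0.37. The smallest planned MM effect is 0.6 − 0.3 = 0.3. By the noncentral t, power is 32% for a difference of 0.3, 79% for 0.5 and 98% for 0.7.

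**Step 3: the full rule.** I required F > 3.034 and both contrasts > 2.359, by simulation from normal arm means and a chi-square pooled variance (1,000,000 trials per combination, SD 1).

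| Both contrasts significant | MM 0.6 | MM 0.8 | MM 1.0 |
|---|---|---|---|
| HYP 0.8 | 30% | 67% | 78% |
| HYP 1.0 | 32% | 78% | 96% |
| HYP 1.4 | 32% | 79% | 98% |

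Taking the values in the order listed (0.8/0.6, 1.0/0.8, 1.4/1.0) gives 30, 78 and 98%, so the range does not depend on crossing them. If one significant contrast is enough, power is 80–100%. If it is enough for both differences to lie in the right direction after a significant F-test, it is also 80–100%.

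**Step 4: split results.** With MM at 0.6, the outcome HYP significant and MM not occurs in 47, 65 and 68% of trials for HYP 0.8, 1.0 and 1.4.

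**Step 5: sensitivity to SD.** For HYP 0.8/MM 0.6 the both-contrasts power is 39% at SD 0.9, 50% at 0.8, 64% at 0.7, 79% at 0.6 and 92% at 0.5. The three combinations at 78–79% reach 80.1–80.6% at SD 0.98. With baseline adjustment, residual SD = SD √(1 − r²), where r is the correlation of baseline with change. From SD 1, r = 0.2 in absolute value gives 0.98 and r = 0.6 gives 0.80. The plan states no r.

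**The case against.** **The quoted sentence is true.** D6z says the calculation used an ANOVA and describes the hypothesis it powered as treatments having different effects. A reader might infer an arithmetic error; there is none. A reader might also infer that the plan promises 80% for MM against ED; it does not. What stands against the plan is the heading and the two other statements, which carry the omnibus figure over to a hypothesis that the omnibus test alone does not decide.

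**The rule is less open than it may look.** Each Veteran receives one treatment, so 'or' is natural wording for a claim about both arms. Aim 1 and the support rule both say 'and'. D6x also anticipates for both arms that "HYP and MM will have significant beneficial effects on outcomes". The hypothesis asks for significantly greater decreases and Tukey is named, so a rule satisfied by direction alone is a weak reading: it would leave the Tukey tests with no part in the decision. I accept this, and it makes both contrasts significant the most natural reading. That is also the reading on which the stated power fails most. A one-arm reading is not excluded: section J speaks of one or both treatments being effective, although that is not a decision rule.

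**The shortfall is concentrated.** SD 1 is the top of a range that starts at 0.15, and the planned ANCOVA may lower the residual SD. A reader might count only two of nine combinations at 80% or more and conclude that the trial is broadly underpowered. That count is fragile, because three of the seven misses are at 78–79% and pass at SD 0.98. The clear shortfall is at MM 0.6. Still, the plan claims adequacy at the largest SD, and at SD 0.8 the power there is only 50%.

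**A split result would be visible arm by arm** in the Tukey output. That limits the harm, but it does not settle what would be said of the primary hypothesis.

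**Conclusion.** The stated 80% is correct for the omnibus test but is not the power of the rule that decides Hypothesis 1. On the most natural reading of that rule, power at SD 1 is 30–32% whenever MM is 0.6, 67% at HYP 0.8/MM 0.8, borderline in three combinations and 96–98% in two. In the weakest case, MM–ED alone has 32%. If one significant arm is enough, the stated figure essentially holds. The wording does not fully exclude that reading, so at MM 0.6 and SD 1 the most likely single outcome, a split result, has no fixed interpretation.

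This rests on a Tukey family-wise level of 0.05 and no gain from baseline adjustment, neither given in the documents. A different level would not rescue the weakest case: with unadjusted pairwise tests after the F-test, its both-contrasts power is 45%. The documents do not support saying that the sample size was miscalculated or that the trial is underpowered on every reading. The point should be fixed because it concerns the primary hypothesis and can be settled in the text.

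**What to change.** (a) Before unblinded analysis, state in the Précis, section A2 and D6x, in the same words, whether Hypothesis 1 needs both contrasts with ED, needs at least one, or is judged separately for each arm. Say whether each comparison must be significant by Tukey, and give the family-wise level.

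(b) In D6z, label the 80% as omnibus power. Add the power of the chosen rule and of each contrast with ED; in the weakest case at SD 1 these are HYP–ED 79%, MM–ED 32% and both 30%. Bring the opening of D6z and the reference to adequate power in D6x into line. A sentence noting that a non-significant MM result at the smallest planned effect is not well-powered evidence of no benefit would prevent misreading.

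The cost is wording: no added participants and no change of test. The one downside is a less favourable stated power if both arms are required. Because the protocol is already at version 23, the change should be dated so that it can be seen to precede unblinded analysis.
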